14.3 Patient Characteristics

Patient characteristics will be summarized by cohort. Patient demographics and disease characteristics will be summarized using descriptive methods such as number and percent for factors measured categorically, and median and range for continuous characteristics.

A detailed summary of patient disposition will be provided, which will include the numbers and proportions of patients enrolled in the study, treated under the protocol, as well as completing the study or discontinuing.

14.4 Treatment Compliance

The numbers of dose reductions or delays, numbers of cycles of treatment received, and dose intensity will be summarized for all treated patients for both study drugs.

14.5 Endpoint Definitions

Rate of DLT: The proportion of patients with DLT in each dose escalation cohort.

Objective response rate (ORR): Objective response will be determined by the best overall response designation (per RECIST 1.1) recorded between the date of first dose of trial therapy and the date of objectively documented disease progression or cessation of trial therapy, whichever occurs first. The objective response rate will be the proportion of patients achieving complete or partial response as their best response to therapy.

Progression-free survival (PFS): Time from start of trial treatment until objective disease progression (per RECIST 1.1) or death, whichever occurs first. Deaths that occur after 12 weeks following the date last known progression-free will not be counted as PFS events. For patients without progression or death within 12 weeks following the date last known progression-free, follow-up will be censored at the date of last disease assessment. Overall survival (OS): Time from start of trial treatment to death from any cause. For patients who are lost to follow-up or who have no documentation of death at the time of final analysis, follow-up will be censored at

the date of last assessment of vital status.

Time-to-progression (TTP): Time interval between the dates of the start of trial treatment and first documentation of progressive disease. In the absence of documented progressive disease, follow-up will be censored at date of last disease assessment. Deaths without prior progression will be censored events.

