2.3.3 Rationale for Endpoints

2.3.3.1 Efficacy Endpoints

The primary endpoint of this study is to determine the safety, tolerability and recommended dosing for the combination of pembrolizumab plus trebananib. Our secondary objective are to obtain in preliminary fashion the efficacy of the combination including PFS at 6 months, the rate of 1-year overall (OS), the response rate (RR) and time to progression in diseases where anti-angiogenesis had shown to be effective. Chest, abdomen, and pelvic CT scan will be obtained every twelve weeks for determination of therapeutic efficacy. Standard solid tumor response criteria (RECIST) will be obtained. To further explore the clinical observations in some patients receiving ipilimumab of delayed responses and disease burden increasing before stable disease or response attained, we will incorporate proposed immune response criteria to assess for clinical activity. These immune response criteria (irRC) (Hodi, Hoos et al. 2008) (Wolchok et al., 2009) will be captured and compared to standard response criteria for solid tumors.

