10.5.2 Follow-Up Visits

Participants who discontinue trial treatment for a reason other than disease progression will move into the Follow-Up Phase and should be assessed every 12 weeks (84 ± 7 days) by radiologic imaging to monitor disease status for at least 1 year. Every effort should be made to collect information regarding disease status until the start of new anti-neoplastic therapy, disease progression, death, end of the study or if the participant begins retreatment with pembrolizumab as detailed in Section 10.5.4. Information regarding post-study anti-neoplastic treatment will be collected if new treatment is initiated.

Participants who are eligible to receive retreatment with pembrolizumab according to the criteria in Section 11.3.4 will move from the follow-up phase to the Second Course Phase when they experience disease progression. Details are provided in Section 9 – Trial Flow Chart for Retreatment.

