11.1.4.3 Evaluation of Best Overall Response

The best overall response is the best response recorded from the start of the treatment until disease progression/recurrence (taking as reference for progressive disease the smallest measurements recorded since the treatment started). The patient's best response assignment will depend on the achievement of both measurement and confirmation criteria.

For Participants with Measurable Disease (i.e., Target Disease)

Target Lesions	Non-Target Lesions	New Lesions	Overall Response	Best Overall Response when Confirmation is Required*
CR	CR	No	CR	> 4 wks Confirmation**
CR	Non-CR/Non-PD	No	PR	≥4 wks Confirmation**
CR	Not evaluated	No	PR	
PR	Non-CR/Non-PD/not evaluated	No	PR	
SD	Non-CR/Non-PD/not evaluated	No	SD	Documented at least once > 4 wks from baseline**
PD	Any	Yes or No	PD	no prior SD, PR or CR
Any	PD***	Yes or No	PD	
Any	Any	Yes	PD	

* See RECIST 1.1 manuscript for further details on what is evidence of a new lesion.
 
** Only for non-randomized trials with response as primary endpoint.
 
*** In exceptional circumstances, unequivocal progression in non-target lesions may be accepted as disease progression.
 
Note: Participants with a global deterioration of health status requiring discontinuation of treatment without objective evidence of disease progression at that time should be reported as “symptomatic deterioration.” Every effort should be made to document the objective progression even after discontinuation of treatment.
				

For Participants with Non-Measurable Disease (i.e., Non-Target Disease)

Non-Target Lesions	New Lesions	Overall Response
CR	No	CR
Non-CR/non-PD	No	Non-CR/non-PD*
Not all evaluated	No	not evaluated
Unequivocal PD	Yes or No	PD
Any	Yes	PD

* ‘Non-CR/non-PD’ is preferred over ‘stable disease’ for non-target disease since SD is increasingly used as an endpoint for assessment of efficacy in some trials so to assign
		

this category when no lesions can be measured is not advised
--

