Overall response using irRC will be based on these criteria:

Immune-Related Complete Response (irCR): Complete disappearance of all tumor lesions (target and non-target together with no new measurable/unmeasurable lesions) for at least 4 weeks from the date of documentation of complete response.

Immune-Related Partial Response (irPR): The sum of the products of the two largest perpendicular diameters of all target lesions is measured and captured as the SPD baseline. At

each subsequent tumor assessment, the SPD of the two largest perpendicular diameters of all target lesions and of new measurable lesions are added together to provide the Immune Response Sum of Product Diameters (irSPD). A decrease, relative to baseline of the irSPD compared to the previous SPD baseline, of 50% or greater is considered an immune Partial Response (irPR).

Immune-Related Stable Disease (irSD): irSD is defined as the failure to meet criteria for immune complete response or immune partial response, in the absence of progressive disease.

Immune-Related Progressive Disease (irPD): It is recommended in difficult cases to confirm PD by serial imaging. Any of the following will constitute progressive disease:

At least 25% increase in the SPD of all target lesions over baseline SPD calculated for the target lesions.

At least a 25% increase in the SPD of all target lesions and new measurable lesions (irSPD) over the baseline SPD calculated for the target lesions. (Hodi, Hoos et al. 2008) (Wolchok et al., 2009)

Table 10. Immune-Related Response Criteria Definitions

Target Lesion Definition	Non-Target Lesion Definition	New Measurable Lesions	New Unmeasurable Lesions	Percent change in tumor burden (including measurable new lesions when present)	Overall irRC Response
Complete Response	Complete Response	No	No	−100%	irCR
Partial Response	Any	Any	Any	≥ −50%	irPR
				<−50% to <+25%	irSD
				>+25%	irPD
Stable Disease	Any	Any	Any	<−50% to <+25%	irSD
				>+25%	irPD
Progressive Disease	Any	Any	Any	≥+25%	irPD

Immune-Related Best Overall Response Using irRC (irBOR)

irBOR is the best confirmed irRC overall response over the study as a whole, recorded between the date of first dose until the last tumor assessment before subsequent therapy (except for local palliative radiotherapy for painful bone lesions) for the individual participant in the study. For the assessment of irBOR, all available assessments per participant are considered.

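### The ORR definition in 14.5 ends at cessation of trial therapy while 11.1.4.3 and irBOR use later cut-offs, so the same scans can give different response rates

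*Combined protocol and SAP*

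**What the plan says.** Three sections of the combined protocol and SAP set a window for best response.

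- **14.5 (ORR):** best overall response by RECIST 1.1, from first dose to "objectively documented disease progression or cessation of trial therapy, whichever occurs first". The rate follows from it: "The objective response rate will be the proportion of patients achieving complete or partial response as their best response to therapy".
- **11.1.4.3 (RECIST best overall response):** the "best overall response is the best response recorded from the start of the treatment until disease progression/recurrence". Treatment stop is not mentioned.
- **11.2.1 (irBOR):** the best confirmed immune-related response, "recorded between the date of first dose until the last tumor assessment before subsequent therapy". Treatment stop is again not a limit.

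Disease assessment continues after treatment. Section 10.5.2 states: "Participants who discontinue trial treatment for a reason other than disease progression will move into the Follow-Up Phase". There they are assessed every 12 weeks "by radiologic imaging to monitor disease status for at least 1 year". Section 5.13 continues disease follow-up for patients who stop without progression, and 5.14 follows those removed for unacceptable adverse events until progression.

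Section 2.3.3.1 brings in immune-related criteria because of "delayed responses and disease burden increasing before stable disease or response attained" in some patients given ipilimumab, and plans to compare them with the standard criteria.

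**The concern.** Two sections define the same RECIST quantity with different end points, and the plan does not say which governs. An analyst following 14.5 and one following 11.1.4.3 could report different ORRs from the same data.

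The 14.5 window also sits badly with the rest of the design. The plan allows for late responses and images patients after they stop without progression, then bars what those images first show from the ORR numerator. Section 5.17 keeps a patient who stops for a drug-related adverse event in the evaluable population, so that patient stays in the denominator. Stopping for toxicity is only one route. The cut applies equally to a patient who completes the planned course or stops for any other reason without progression.

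The planned comparison of RECIST with immune-related response is affected too. Part of any difference would come from one criterion stopping at the end of treatment while the other runs on, not from the criteria themselves.

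**Working it through.** **Step 1. One patient under each window.** Take a patient who stops without progression, has stable disease on the End of Treatment CT, and first reaches the 30% decrease for PR on a later follow-up scan, before progression or any new therapy.

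| Rule | Is the later scan inside the window? | RECIST best response |
|---|---|---|
| 14.5 | No, trial therapy has ceased | SD, non-responder |
| 11.1.4.3 | Yes, no progression yet | PR, responder |
| 11.2.1 (irBOR) | Yes, no subsequent therapy yet | Not applicable; the scan is available to irBOR |

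If the PR is already visible on the End of Treatment CT listed in the Section 9 calendar, it can count under all three. The conflict therefore concerns responses first seen after stopping.

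**Step 2. Direction.** The 14.5 window lies inside the 11.1.4.3 window: same start, and an end that is never later. Every responder under 14.5 is a responder under 11.1.4.3, but not the reverse. With the same denominator, ORR(14.5) ≤ ORR(11.1.4.3).

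**Step 3. Scale of one responder.** The plan gives no ORR target to reproduce. The interim rate in 14.2 checks: 1/15 = 6.7%, stated as 7%. One reclassified patient moves ORR by 1/n: 1/12 = 8.3 percentage points, 1/40 = 2.5. Section 14.6 specifies exact binomial 90% intervals:

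| n | Responders | ORR | Exact 90% CI |
|---|---|---|---|
| 12 | 1 | 8.3% | 0.4% to 33.9% |
| 12 | 2 | 16.7% | 3.0% to 43.8% |
| 40 | 3 | 7.5% | 2.1% to 18.3% |
| 40 | 4 | 10.0% | 3.5% to 21.4% |

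The 40 is the CRC total in 14.2 (15 already enrolled plus 25).

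**Step 4. Illustration of bias (assumed inputs).** The documents do not give the share q of responders first documented after stopping. With ORR p under the 11.1.4.3 window, the 14.5 rate is p(1 − q), and n·p·q responders are expected to be missed. Assuming p = 15%:

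| q | ORR under 14.5 | Missed, n=12 | Missed, n=40 |
|---|---|---|---|
| 5% | 14.3% | 0.09 | 0.3 |
| 10% | 13.5% | 0.18 | 0.6 |
| 20% | 12.0% | 0.36 | 1.2 |

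These figures show scale only and do not estimate the bias in this trial.

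**The case against.** The strongest case is that an on-treatment response window is a legitimate, conservative choice that was specified in advance. ORR is secondary, 14.6 calls the within-disease analyses mainly descriptive, and no decision rests on ORR. Late responses are not lost to the trial, because irBOR can use them, and PFS, TTP and OS have no cut at treatment stop. The exposed group is also smaller than all patients with toxicity: 5.3.3.1 and 5.3.3.2 let one drug continue when the other is stopped, so trial therapy need not have ceased.

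All of this stands, and it limits the importance of the point. It does not remove the conflict with 11.1.4.3, and the plan gives no reason for the earlier cut.

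Three stronger readings are tempting, and the documents do not support them.

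- **A patient who stops before the week-12 scan can never be a responder.** The calendar lists a CT at the End of Treatment visit, so a response visible then can count.
- **A PR on the last on-treatment scan is lost for want of confirmation.** Section 11.1 schedules confirmatory scans at 4-6 weeks, but the footnote in 11.1.4.3 limits the confirmation requirement to non-randomized trials with response as primary endpoint. Response is secondary here. The text is not fully clear, but it does not establish that such a PR is lost.
- **The tested DCR loses power.** Section 14.2 defines DCR without a cut at treatment stop, and 11.1.5 measures stable disease until progression criteria are met. Any effect would fall mainly on late CR or PR. The earlier ipilimumab plus bevacizumab trial in melanoma (2.1.3) had 5 of 46 patients (10.9%) come off for toxicity. Carried over as an assumption, that is 40 × 0.109 = 4.3 CRC patients exposed, not successes lost. At a 30% DCR the whole exposed group would hold about 4.3 × 0.30 = 1.3 successes, and at the interim response rate about 4.3 × 0.067 = 0.3 responders.

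**Conclusion.** The inconsistency is real and follows from the text alone. Sections 14.5, 11.1.4.3 and 11.2.1 use three windows, no passage reconciles them, and the planned RECIST versus immune-related comparison would mix them. Taken as written, 14.5 excludes from the ORR numerator any response first seen after a stop without progression, although the imaging is collected.

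Relative to 11.1.4.3 the bias can only be downward. The documents give neither a rate of stopping without progression in this trial nor a rate of first response after stopping, so its size cannot be stated beyond the per-responder steps above. Those steps matter most in the ovarian cohort of 12.

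The consequence is confined to a secondary, descriptive endpoint. For DCR the plan leaves the window of best RECIST response unstated. That is an ambiguity to close, not a demonstrated loss of power. The correction is worth making because it is specific and cheap.

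**What to change.** In 14.5, replace the cut at the end of trial therapy with the start of new anti-cancer therapy. Best response then runs from first dose to the earlier of documented progression or new anti-cancer therapy, with the Second Course Phase excluded, in line with 10.5.4. Use the same window in 11.1.4.3 and for best RECIST response in the DCR definition in 14.2. The comparison with irBOR would then no longer depend on when treatment stopped.

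If the on-treatment window is preferred, state the reason in 14.5, reconcile 11.1.4.3 with it, and report the ORR to progression or new therapy alongside.

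The cost is one phrase in 14.5 and matching edits in the other two places. No new scans are needed, since 10.5.2 already provides for them. The downside is that the 15 interim CRC patients must be re-checked under the same rule so that all 40 are classified alike.

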Post Treatment

	Post-Treatment			
Treatment Cycle/Title:	End of Treatment Visit	Safety Follow-up	Follow Up Visits	Survival Follow-Up
Scheduling Window (Days):	At time of Discontinuation	30 days post discontinuation (± 3)	Every 12 weeks post discontinuation (± 7) for at least a year	Every 12 weeks (± 7)
Prior and Concomitant Medication Review	x	x		
Post-study anticancer therapy status			x	X
Survival Status				x
Review Adverse Events	x	x	x	
Physical Examination	x	x	x	
Vital Signs and Weight	x	x	x	
ECOG Performance Status	x	x	x	
CBC with Differential	x	x		

Comprehensive Serum Chemistry Panel, lipase and amylase	x	x		
Urinalysis ^B		x		
T3, FT4 and TSH		x		
Chest, Abdomen and Pelvic CT scan ^C	x		x	
Brain MRI ^D	x		x	
Archival or Newly Obtained Tissue Collection ^G	x			
Correlative Studies Blood Collection ^G	x			

^A For women of child-bearing potential, a negative serum β -HCG pregnancy test must be performed during screening. A urine pregnancy test should be performed within 24 hours of starting treatment. A urine pregnancy test may be performed at all other timepoints. If a urine pregnancy test result is positive, a serum pregnancy test must be completed and resulted as negative for a participant to receive treatment.

^B Proteinuria will be monitored by urine protein: creatinine ratio at least every six weeks. If appropriate, 24-hour urine collection for protein may be obtained.

^C CT scan of the chest, abdomen, and pelvis will be performed every 12 weeks (\pm 7 days)

^D Brain MRI to be performed only on melanoma and RCC patients. Brain MRI should be performed during screening. Repeat brain MRI should be performed if there are any neurological symptoms or findings. Brain MRI with and without contrast is preferred. If a patient is not able to obtain an MRI, CT imaging with contrast is acceptable. If a patient is not able to receive IV contrast, CT head without contrast is acceptable.

^E Imaging for baseline tumor assessment is to be performed within 28 days prior to the start of study registration.

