Repeat scan confirms PD	No additional imaging required	Discontinue treatment	No additional imaging required	N/A
Repeat scan shows SD, PR, or CR	Continue regularly scheduled imaging assessments every 12 weeks	Continue study treatment at the Investigator's discretion	Continue regularly scheduled imaging assessments every 12 weeks	May restart study treatment if condition has improved and/or clinically stable per Investigator's discretion
Tumor imaging will be assessed every 12 weeks (84 ±7 days).				

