11.1.7 Progression-Free Survival

Overall Survival: Overall Survival (OS) is defined as the time from randomization (or registration) to death due to any cause, or censored at date last known alive.

Progression-Free Survival: Progression-Free Survival (PFS) is defined as the time from randomization (or registration) to the earlier of progression or death due to any cause. Participants alive without disease progression are censored at date of last disease evaluation.

Time to Progression: Time to Progression (TTP) is defined as the time from randomization (or registration) to progression, or censored at date of last disease evaluation for those without progression reported.

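### Sections 14.5 and 11.1.7 define PFS incompatibly, and the 12-week death window in 14.5 is shorter than the permitted gap between scans

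*Combined protocol and SAP*

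**What the plan says.** Section 14.5 (Endpoint Definitions) defines PFS as "Time from start of trial treatment until objective disease progression (per RECIST 1.1) or death, whichever occurs first". It then restricts which deaths count: "Deaths that occur after 12 weeks following the date last known progression-free will not be counted as PFS events". For a patient with no progression and no death inside that limit, "follow-up will be censored at the date of last disease assessment".

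Section 11.1.7 says "Progression-Free Survival (PFS) is defined as the time from randomization (or registration) to the earlier of progression or death due to any cause", and on censoring, "Participants alive without disease progression are censored at date of last disease evaluation". It sets no limit on how long after a scan a death may fall.

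On timing, Table 7 in Section 11.1.6 says "Tumor imaging will be assessed every 12 weeks (84 ±7 days"), and Section 11.1 gives the same interval. Footnote E of the study calendar in Section 9 says "Imaging for baseline tumor assessment is to be performed within 28 days prior to the start of study registration". Section 11.1.3 also caps the baseline evaluation at four weeks before treatment.

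Section 1.3 lists 6-month PFS as a secondary objective. Section 14.6 reports it by disease as a Kaplan-Meier estimate with a 90% confidence interval, and describes the within-disease analyses as mainly descriptive. No sentence says which of the two definitions governs. Section 14.5 does not say what the last progression-free date is for a patient who has had no on-study scan.

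**The concern.** The two sections differ on the time origin and on which deaths are events. Two analysts who each follow the protocol could report different 6-month PFS values from the same data.

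The window in 14.5 also looks like a missed-assessment rule, meant to stop a death being credited long after disease status was last known. Such a rule should act only when an assessment was missed. Here it equals one nominal scan interval and leaves no room for the ± 7 day tolerance, so it can act on fully compliant patients. Those patients are censored back at their last scan, and a death without a recent scan is plausibly related to prognosis. At stake is a secondary estimate in small cohorts, where one reclassified patient is visible.

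**Working it through.** The protocol states no expected value or precision for 6-month PFS, so there is no figure of its own to reproduce.

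**1. Window against schedule.** Inputs: a 12-week window = 12 × 7 = 84 days (14.5); scans every 84 ± 7 days (11.1.6); baseline scan up to 28 days before treatment (Sections 9 and 11.1.3).

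- On-time scan, then a scan 7 days late: 84 + 7 = 91 days.
- Scan 7 days early, then a scan 7 days late: 84 + 7 + 7 = 98 days.
- Baseline scan 28 days before treatment to a late first on-study scan: 28 + 84 + 7 = 119 days.

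All three exceed 84. Between on-study scans, a death on days 85 to 98 can be excluded with nothing missed. In the first interval the result depends on the undefined reference date. Counted from first dose, only deaths on days 85 to 91 are exposed. Counted from a baseline scan 28 days earlier, the window closes on day 84 − 28 = 56, so deaths from day 57 to the first scan are exposed. Such a patient is censored at or before time zero and contributes nothing.

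**2. Size of one excluded death, n = 12** (the ovarian cohort, Section 14.1). Suppose six patients have events by day 84 and six are at risk afterwards.

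- *Death before 6 months.* One patient has a clean day-84 scan and dies on day 170, inside the window for the next scan (168 + 7 = 175). Since 170 − 84 = 86 > 84, 14.5 excludes the death and censors at day 84. The 11.1.7 rule gives 0.5 × 5/6 = 5/12 = 41.7%; 14.5 gives 50.0%. The shift is +8.3 points.
- *Death after 6 months.* The same patient has no scan after day 84 and dies on day 250; another patient progresses on day 168. The 11.1.7 rule gives 0.5 × 5/6 = 41.7%. Under 14.5 the first patient left the risk set at day 84, giving 0.5 × 4/5 = 40.0%. The shift is −1.7 points.

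With no earlier censoring, and no other event between the last scan and month 6, an excluded early death moves the estimate by 1/n: 1/12 = 8.3 points, or 1/40 = 2.5 points at the CRC target of 40 (Section 14.2).

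**3. Net direction, by simulation.** Both death rules were applied to the same 60,000 patients per scenario, with Kaplan-Meier at 182.6 days. These inputs are assumptions, not document figures: exponential latent progression, median 90 to 180 days; exponential death before progression, median 150 to 450 days; death hazard doubled after progression; 0 to 10% of scans missed at random; 0 to 40% of patients stopping imaging at progression without a scan.

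| Imaging | Patients whose death is excluded | 14.5 minus 11.1.7, 6-month PFS |
|---|---|---|
| Full adherence, reference = first dose | 1–2% | +0.1 to +0.2 points |
| Full adherence, reference = baseline scan | 4–7% | +0.8 to +1.1 points |
| 10% missed at random, either reference | 5–11% | −0.2 to +1.3 points |
| 10% missed and 20–40% stop at progression | 13–32% | −0.9 to −8.8 points |

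In the last row the sign reverses because 11.1.7 carries an unscanned progressor as event-free until a late death, while 14.5 removes that patient at the last scan. Both rules overestimated latent 6-month PFS in all 32 scenarios, partly because progression is seen only at scans.

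**The case against.** Limiting how long after the last assessment a death may count is a legitimate design choice, and Section 14 is where a reader would naturally look for the governing definition. The reference to randomization in 11.1.7 of a non-randomised trial reads as generic text. The plan also has safeguards against unscanned deaths: CT at the end-of-treatment visit (Section 9), continued 12-weekly imaging for patients who stop without progression (10.5.2), and an instruction to try to document objective progression after discontinuation (11.1.4.3). The consequence is modest. PFS is descriptive, and the CRC expansion is sized on disease control. If 6-month PFS were 40%, an approximate log(−log) 90% interval would be 18–62% with 12 patients and 27–52% with 40.

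Most of this stands, and it limits the weight of the point. It does not remove the contradiction, since nothing says 14.5 takes precedence. Nor does it justify a window that discards deaths when every scan was on time.

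A reader might infer that the 14.5 rule biases 6-month PFS upward in general. The documents do not support that. The effect is upward for excluded deaths before 6 months, but the net difference from 11.1.7 was close to zero with imaging maintained and negative when many patients stopped imaging. In those last scenarios 14.5 was the closer of the two to latent PFS. A reader might also take the loss of deaths from day 57 as certain. It follows only if the undefined reference date is read as the baseline scan.

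**Conclusion.** The point holds as an inconsistency plus a mis-set window. The contradiction between 14.5 and 11.1.7 and the 84-against-98-day mismatch follow directly from the text and need no assumption. The exposure from day 57 is conditional on how the last progression-free date is read.

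The size of the effect on 6-month PFS cannot be fixed from the documents. It depends on imaging adherence, and the simulated range of −8.8 to +1.3 points rests on the assumptions listed above. The firm figure is the exact example: in a cohort of 12, one excluded death can shift the estimate by 8.3 points. The difference in time origin is not quantified, because the protocol gives no fixed interval from registration to first dose. The matter should be corrected, but PFS carries no test or decision rule, so it does not threaten the trial's main conclusions.

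**What to change.** Use one definition in both sections: time from first dose to RECIST 1.1 progression or death from any cause. Align 11.1.7 to the first-dose origin and remove the 12-week sentence from 14.5. The case for counting all deaths is that no observed event is lost to scan timing and the result is reproducible; it is not that this rule is less biased in every scenario.

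If a missed-assessment window is kept, make it longer than the largest permitted gap between on-study scans, so more than 98 days. Two intervals with both tolerances, 2 × 84 + 7 + 7 = 182 days, would do. Measure the first interval from first dose, state this for patients with no on-study scan, and report 6-month PFS counting all deaths as a sensitivity analysis.

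The cost is wording in two sections, best settled before the final analysis. The 6-month estimate may move slightly in either direction.
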